16.5 Neurocognitive assessments

Age-adjusted domain and composite scores for each neurocognitive instrument will be calculated using available methods.

The individual patient overall/domain/sub-scores for each neurocognitive assessment instrument will be expressed as an individual's Z-score (i.e. an indication of how many standard deviations a domain score is from the mean) and compared to reference ranges from normative data for children and young adults with haemophilia (adjusted for appropriate identified covariates) (HAEM-4436, eTHINK study). All the scores will be provided by a CRO. The individual score versus time of exposure (years) will be presented graphically per patient.

In addition, all data and scores will be summarised and listed.

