### 8.2. Scheduled Visits

**Table 1: Visit Schedule for Neurocognitive Assessments**

Visit Number	Scheduled Interval	Analysis Visit
1, 20, 23, 26, 28-50	
 
BRIEF: Every 6 months (all countries)
 
██████ Battery: Every 6 months (all countries)
 
SDH: Every 6 months (all countries)
 
HH: Every 6 months (all countries)
 
Bayley-III / WPPSI-IV / WASI-II: Every 1 year (English-speaking countries only)
 
ABAS-3: Every 1 year (English-speaking countries only)
 
BASC: Every 1 year (English-speaking countries only)
 
	Yes
End of Trial		Yes
Unscheduled Visit		No

Study visits will be renamed such that the first visit is “Initial Assessment”, the next is “Assessment 2”, the following is “Assessment 3”, and so on, to account for the fact that not all subjects will be starting their neurocognitive assessments

at the same visit. If patients start on pre-prophylaxis and switch to prophylaxis at Visit 20, the assessments will be displayed under “Prophylaxis” in the tables.

The patient’s age when the Structured Developmental History (SDH) is completed will be used as the Visit Age for each visit.

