### 10.2. Initial Assessment Definition

Initial Assessment data is the first assessment that has cognitive data for each subject. This first set of cognitive data may occur at different visits depending on the subject.

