### 12.2. Analyses

Cognitive outcome measures from the neurocognitive instruments will have a series of z-scores calculated. This includes age-adjusted US normative (international normative for [REDACTED] computerized tests) z-scores (see Section 10.6.1), age-adjusted hemophilia z-scores (see Section 10.6.3), z-score change from prior (for both age- and hemophilia-adjusted z-scores), and z-score change from Initial Assessment (for both hemophilia- and age-adjusted z-scores). The above z-scores will be tabulated descriptively (n, mean, standard deviation, median, interquartile range (first quartile, third quartile), min, max).

Individual domains/scores by visit will be plotted per patient for each instrument.

A subject listing including scores, z-scores (age- and hemophilia-adjusted), change from prior z-scores (age- and hemophilia-adjusted) and change from initial assessment z-scores (age- and hemophilia-adjusted) on each neurocognitive instrument and outcome measure will be generated. All z-scores will be adjusted so that positive scores reflect improvement.

All analyses will be done in SAS (v9.4).

See Appendix 1 for an example of the tables, listing, and figures (TLF).

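### SAP 12.2 plots neurocognitive scores by visit where protocol 16.5 calls for time of exposure in years, and the SAP's assessment numbers do not stand in for exposure

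*SAP*

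**What the plan says.** Protocol 16.5 names the time scale of the individual graph: "The individual score versus time of exposure (years) will be presented graphically per patient". For the rest of the neurocognitive output it says only "In addition, all data and scores will be summarised and listed", with no time scale. Protocol 3.4 gives the reason for these assessments: a theoretical safety concern about PEG, and the potential clinical effects of longer-term exposure to N9-GP.

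SAP 12.2 specifies a different graph: "Individual domains/scores by visit will be plotted per patient for each instrument". On tables it says "The above z-scores will be tabulated descriptively", covering z-scores, change from the prior assessment and change from Initial Assessment. The subject listing holds the scores, the z-scores and the same two changes. Neither is given an exposure-time column or stratum.

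SAP 8.2 states "Study visits will be renamed such that the first visit is" Initial Assessment, followed by Assessment 2, Assessment 3 and so on, "to account for the fact that not all subjects will be starting their neurocognitive assessments" at the same visit. SAP 10.2 confirms the consequence: "This first set of cognitive data may occur at different visits depending on the subject". The only patient-level time variable that the SAP defines is Visit Age (SAP 8.2), which is age and not exposure. SAP section 6 presents the document as an elaboration of the protocol's analysis and declares no departure from it.

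**The concern.** The graph in protocol 16.5 is the only neurocognitive output that either document ties explicitly to exposure. The trial has one arm and no formal sample size calculation (protocol 16.1), and the neurocognitive analysis is descriptive. A display of score against exposure is therefore the most direct way for a reader to see whether scores drift as exposure accumulates.

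If the x-axis is an assessment number counted from each child's first test, two children at the same point on the axis may have very different exposure, and the steps along it are unequal in time. The plots would be produced as specified and still not show what the protocol set out to show.

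**Working it through.** The documents state no figure for this point, so there is none to reproduce. The check is how much exposure time one assessment number can cover.

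**Inputs**
- Exposure day (ED) at each visit, from protocol Table 2-1 and sections 8.1.3 to 8.1.8: V1 = ED 1, V20 = ED 20, V23 = ED 50, V26 = ED 80, V28 = ED 100, V29 = ED 124.
- Assessment visits for the all-country instruments, from protocol Table 8-1: V1, V20, V23, V26, V28, V29 and all later visits.
- Planned first assessment, from protocol 8.3.3: the first visit after age 1 or age 2, depending on country. The all-country instruments start from age 2 (Table 8-1).
- Age at entry: under 6 years (protocol 6.2).

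**Assumption.** Strictly weekly dosing from V1, with no extra doses and no pre-prophylaxis. ED n then falls n − 1 weeks after the first dose, and years = (n − 1) × 7 / 365.25.

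| Visit | ED | Weeks since first dose | Years | Gap from previous assessment (weeks) |
|---|---|---|---|---|
| V1 | 1 | 0 | 0.00 | – |
| V20 | 20 | 19 | 0.36 | 19 |
| V23 | 50 | 49 | 0.94 | 30 |
| V26 | 80 | 79 | 1.51 | 30 |
| V28 | 100 | 99 | 1.90 | 20 |
| V29 | 124 | 123 | 2.36 | 24 |

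**Spread within one assessment number**
- Initial Assessment: 0.00 years if first tested at V1, 1.90 years if first tested at V28.
- Assessment 2: 0.36 years for the first child (V20), 2.36 years for the second (V29).

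**Can these cases occur?** A child who enrols at age 2 or later can be tested at V1. A child on the all-country schedule who is first tested at V28 has just turned 2, so was first dosed at about 2.00 − 1.90 = 0.10 years of age. Both fit the entry and testing rules. A first test at V29 (2.36 years) would need a first dose earlier still. In English-speaking countries testing starts from age 1, so under the planned rule the spread at Initial Assessment is narrower there.

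**Do the original visit numbers serve instead?** Only roughly. They track exposure days, not years. Protocol 5.3.2 and 8.1.1.1 allow on-demand dosing, or intervals longer than a week, until 20 EDs or 24 months of age. For a child first dosed in early infancy, V20 may then come about 2 years after V1 rather than 19 weeks after it, and that delay carries into every later visit.

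**The case against.** The strongest case for leaving the SAP alone has four parts.

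- **Order is kept.** Within one child's plot, assessments still run in order of increasing exposure, and change from Initial Assessment is tabulated and listed. Scheduled visits are tied to exposure days and dosing dates are collected. A reader might infer that an exposure effect cannot be read from the trial at all. The documents do not support that, because exposure time is derivable. What is missing is an output that shows it.
- **The tables do not contradict the protocol.** A reader might infer that they do. Protocol 16.5 fixes exposure time for the individual graph only, and SAP 12.2 does not name the tables' row variable. Tabulation by assessment number is itself inferred from SAP 8.2.
- **The by-visit plot may be an addition.** The SAP declares no departure. Its example figures are in Appendix 1, which is not in the text available. SAP version 2.0 (15 July 2019) is 113 days older than protocol version 8.0 (5 November 2019), so the documents do not show whether the exposure wording was in the version that the SAP followed. These points may explain the mismatch. They do not remove it: the current protocol names one axis and the SAP another.
- **Signals are found elsewhere.** Individual results are compared with eTHINK norms and go to an expert panel (SAP 10.3, protocol 8.3.3). That stands, and it limits the consequence.

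A reader might also reason that the computerised battery starts at age 4, so a child dosed since age 1 and a child newly enrolled at 4 would both take it at Initial Assessment, with about 3 years of exposure against none. That does not follow. SAP 10.2 defines Initial Assessment per subject, not per instrument. On the planned schedule the first child would already have been tested at about age 2, or at age 1 in English-speaking countries, so the battery would come under a later assessment number.

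**Conclusion.** The point holds for the individual graph. Protocol 16.5 and SAP 12.2 specify different x-axes, and the SAP's renumbering means that its axis is not a proxy for the protocol's. On nominal weekly dosing, children sharing an assessment number can differ by about 1.9 to 2.0 years of exposure, and successive points are 19 to 30 weeks apart. The specified output neither shows scores against exposure time nor lines children up by it.

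The size rests on weekly dosing from V1 and on first tests falling at V1 and V28. How many children lie near those extremes is not known from the documents. Pre-prophylaxis would change the figures.

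The outputs are descriptive and lie outside the endpoints listed in protocol 4.2, so the primary endpoint is untouched. The correction is still worth making, because it restores an explicit protocol commitment on the question that the assessments were added to answer.

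**What to change.** In SAP 12.2:

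1. Define time of exposure at each neurocognitive assessment as years from the first N9-GP dose to the assessment date.
2. Use it as the x-axis of the per-patient plots, as protocol 16.5 states.
3. Add it to the subject listing. Cumulative exposure days could be listed beside it, since the two diverge during pre-prophylaxis.
4. If the by-visit plot is kept, describe it as additional to the protocol's graph. If the exposure graph is to be produced outside this SAP, say where.

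SAP section 6 allows version-controlled revision before database lock. No new patients, visits or assessments are needed. The first injection's date is already recorded in the eCRF (protocol 8.5), while the neurocognitive data are processed by a CRO (protocol section 14). The work is therefore to pass one first-dose date per child across and merge it, plus dosing counts if exposure days are listed.

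Tables by exposure window are optional. The protocol does not ask for them. With about 40 expected completers split across age-specific instruments, their cells would be small and exposure would be confounded with age.
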